8.8 Efficacy Analyses

The statistical analysis of the primary endpoint for this study will be performed after the last patient has completed the Week 28 response assessment. All efficacy data will be analyzed at this time, plus all PK, PD, immunogenicity, and safety data available at the time of data

cut-off, and these data will be reported in the CSR (Week 28 CSR). After the last patient has completed Week 52 of the study, a CSR addendum (Week 52 CSR) will be prepared to report the additional safety data.

Efficacy will be assessed centrally as CR, PR, SD, and PD, as defined in IWG criteria 2007, and TTE. The main efficacy endpoint will be the difference in ORR (CR+PR) at Week 28, approximately 24 weeks after the completion of study treatment. The efficacy analyses will be applied for both the PP set and FAS. FAS will be considered as primary efficacy analysis population and analysis in PP set will be conducted as a sensitivity analysis.

In FAS, patients without a response assessment at Week 28 will be handled using a conservative approach by imputation using drop-out reason (IUDR), where Non-responder imputation (NRI) method in case of treatment related reasons and otherwise multiple imputation (MI) procedure assuming missing at random (MAR) will be applied. For the PP set, all available data will be used for analysis.

Potential withdrawal reasons are considered as follows based on previous studies; The major reason of missing response assessment at Week 28 is assumed to be either the start of new treatment of FL due to lack of efficacy or toxicity based on Ardeshtna et al. In such reasons related to treatment (i.e. treatment failure requiring tumor targeting treatment for FL other than the protocol-defined treatment, death due to progressive disease), patients without a response assessment at Week 28 will be handled as non-responders. Missing responses unrelated to treatment (i.e. withdrawal by subject, pregnancy) as seen in the Colombat et al. would be considered ignorable missing at random (MAR) and multiple imputation procedure using logistic regression method will be used to impute the missing response assessment at Week 28 (responder versus non-responder). No imputation will be applied when the reasons are unknown whether they are related to treatment or not (i.e. lost to follow-up).

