## 16. Efficacy Outcomes

### 16.1. PRIMARY EFFICACY

#### 16.1.1. PRIMARY EFFICACY VARIABLE & DERIVATION

The primary efficacy variable is the difference in Overall Response Rate (ORR) at Week 28, approximately 24 weeks after the completion of study treatment.

ORR is defined as the proportion of patients with complete response (CR) or partial response (PR) as assessed by central imaging review per IWG criteria 2007 until Week 28 after the start of treatment. ORR will be evaluated for each patient separately from the date of first administration of trial medication (i.e. Day 1) until either progression, death or up to Week 28 (i.e. study day 204 = 190+14), whichever happens earlier. Per protocol, CT scan (neck, chest, abdomen, pelvis, and any other areas known or suspected to be involved) with contrast to be conducted at screening, Week 12 and Week 28 (assessment permitted up to 4 weeks prior to, or 2 weeks after the Weeks 12 and 28 visit).

Patients who start subsequent anticancer therapy will typically have progressed or stopped treatment due to unacceptable toxicity. A CT scan should be conducted at their early treatment discontinuation visit. In the case where a patient starts subsequent anti-cancer therapy but the ORR evaluation period of that patient is still ongoing, the patient's ORR will be evaluated only until the start of subsequent anti-cancer therapy.

Unscheduled assessments recorded during the evaluation period for ORR will be taken into account for determination of ORR. Tumor assessments started on study day 204 but not completed on study day 204 will be fully included in the evaluation of best ORR.

The primary endpoint will be analyzed as described in section 16.1.3 and sensitivity analyses for the primary efficacy analysis will be performed as described in section 16.1.4.

---

Document:

Author:

Version Number:

Version Date:

Final v1.0

10Sep2019

Template No: CS\_TP\_BS016 Revision 4

Effective Date: 01Apr2016

Reference: CS\_WI\_BS005

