### **16.1.2. MISSING DATA METHODS FOR PRIMARY EFFICACY VARIABLE**

The imputation of ORR will follow Imputation Using Drop-out Reason (IUDR). The imputation rules for the IUDR imputation of ORR will be as follows:

Following the start of a new treatment for FL, either due to lack of efficacy or treatment-related toxicity reasons (i.e. treatment failure requiring tumor targeting treatment for FL other than the protocol-defined treatment or death due to progressive disease), patients without a response assessment at Week 28 will be considered as non-responders.

Overall tumor assessments by central imaging review will be assessed as CR, PR, stable disease (SD), progressive disease (PD), Unknown, and No Evidence of Disease (NED). Missing or non-evaluable response assessments (i.e. UNK and NED) will not be imputed and will be considered as non-responders.

Missing responses unrelated to treatment (i.e. withdrawal by patient, pregnancy) will be considered ignorable missing at random (MAR) and multiple imputation procedure using logistic regression method will be used to impute the missing response assessment at Week 28 (responder versus non-responder).

No imputation will be applied when the reasons are unknown for treatment related or not (i.e. lost to follow-up).

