#### Time to event (TTE)

The time to event (TTE) is defined as the time from the date of randomization to the date when an event occurs; the following are considered as an event: disease progression evaluated based on tumor assessment done by central imaging review vendor, death due to any cause, or the start of new treatment for FL, whichever comes first.

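### The primary analysis names only death from progressive disease as a non-response, so a death judged unrelated to treatment can be multiply imputed as a response

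*SAP*

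**What the plan says.** The primary analysis uses the FAS and imputes a missing Week 28 response according to the reason for drop-out (SAP 16.1.2, 16.1.3 and Table 1; Protocol 8.8). SAP 16.1.2 has four rules:

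- **Non-response** for patients without a Week 28 assessment who have started new FL treatment for lack of efficacy or treatment-related toxicity. A bracket explains this as "treatment failure requiring tumor targeting treatment for FL other than the protocol-defined treatment or death due to progressive disease".
- **Non-response** for certain central-review readings: "Missing or non-evaluable response assessments (i.e. UNK and NED) will not be imputed and will be considered as non-responders".
- **Multiple imputation**: "Missing responses unrelated to treatment (i.e. withdrawal by patient, pregnancy) will be considered ignorable missing at random (MAR").
- **No imputation**: "No imputation will be applied when the reasons are unknown for treatment related or not (i.e. lost to follow-up").

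Protocol 8.8 has the same bracket, with the same single kind of death. It also states a general default: non-response for treatment-related reasons, and "otherwise multiple imputation (MI) procedure assuming missing at random (MAR) will be applied". The footnote to SAP Table 1 repeats the three-way split by relatedness and does not mention death.

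Two other passages bear on death. SAP 16.1.1 evaluates ORR from Day 1 "until either progression, death or up to Week 28 (i.e. study day 204 = 190+14), whichever happens earlier", and says that scans begun on day 204 but completed later "will be fully included in the evaluation of best ORR". The secondary time-to-event endpoint counts "death due to any cause, or the start of new treatment for FL, whichever comes first".

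**The concern.** A patient who has died has no Week 28 tumor response. That is an outcome, not a value that exists and went unrecorded, so imputing it from survivors under missing at random has no sound meaning. The rule names one kind of death and leaves the rest to a judgement of relatedness. Two patients who die on the same day could be handled differently in the primary endpoint because one death was labelled related and the other not.

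The equivalence decision is at stake. If such deaths are more frequent on the arm with the lower response, imputing responses for them narrows the observed difference and makes equivalence easier to declare.

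**Working it through.** **Where each kind of death goes.** Cases are deaths before the Week 28 assessment with no response recorded for that visit.

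| Death | Text that applies | Result |
|---|---|---|
| Due to progression | Bracket in SAP 16.1.2 and Protocol 8.8 | Non-response |
| Study-drug toxicity | Not named; treatment-related under Protocol 8.8 and the Table 1 footnote | Can be read as non-response |
| Relatedness unknown | Last rule of SAP 16.1.2; Protocol 8.8 | Not imputed |
| Unrelated, not progression | Unassigned in SAP 16.1.2; default in Protocol 8.8 and the Table 1 footnote | Multiple imputation, so possibly a response |
| Any of these after CR or PR at Week 12 | SAP 16.1.1, if read as best response up to death | Possibly an observed response, no imputation |

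Neither document says who judges relatedness for this purpose. If the adverse-event label of Protocol 6.8 is used, an event that can be expected from age, concurrent illness or medical history is unrelated. A cardiac death in an older patient could then reach the fourth row.

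**The plan's own figure.** Inputs (SAP 2.3): 154 per arm, ORR 77% in both arms, margin 16.0 points, two-sided 95% CI. The normal approximation is power = 2Φ(margin/SE − 1.96) − 1, with SE = √(2 × 0.77 × 0.23/154) = 0.048. This gives 83.1%. Exact enumeration of the unstratified Newcombe-Wilson interval gives 84.0%. At 147 per arm the two methods give 80.6% and 81.3%. The stated 83% and 80% are reproduced.

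**Size per death.** Assume that the imputed response probability equals the planned ORR of 0.77. One imputed death adds 0.77/154 = 0.50 point to its arm's ORR on average, and at most 1/154 = 0.65 point.

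**Assumed split of 4 v 0.** The documents give no rate for such deaths, so this is illustrative. With survivors responding at 77% in both arms, counting the four as non-responses gives 0.77 × 150/154 = 75.0% against 77.0%, a 2.0-point gap. Imputation gives no gap on average. The masked part is 2.0 of 16 points.

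**When it could change the decision.** With 119/154 responders on MabThera, SAIT101 passes with 110/154 or more (difference −5.8 points, lower limit −15.5%, unstratified). A few patients matter only close to that boundary.

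**Chance of wrongly declaring equivalence.** Suppose the true rates with deaths as non-responses are 61% and 77%, and such deaths occur only on SAIT101 at rate d. Non-response gives 2.7%. Imputation raises the SAIT101 rate to 0.61/(1 − d), that is 0.616, 0.622 and 0.629 for d = 1%, 2% and 3%. The chance becomes about 3.5%, 4.6% and 5.9%. This is approximate, because the imputed arm is treated as a full-sample binomial at the survivors' rate.

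**Direction.** If both arms have the same death rate d and survivors respond at p1 and p2, imputation estimates p1 − p2, while non-response estimates (1 − d)(p1 − p2). With balanced deaths, counting them as non-responses shrinks the difference slightly. If the excess falls on the higher-response arm, imputation keeps the arms further apart.

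**The case against.** The strongest reply is that relatedness, not the bracket, governs the rule. Several plausible causes of non-progression death, such as infusion reactions, PML and serious infection, are adverse events of special interest for this drug (Protocol 6.4) and would naturally be classed as treatment-related. A reader might infer that every death other than from progression is imputed as a response. The documents do not support that: toxic deaths can be read as non-responses, deaths of unknown relatedness are not imputed, and the SAP's examples for multiple imputation are withdrawal and pregnancy, not death. This stands, and it confines the gap to deaths judged unrelated. It does not close it, because the Protocol's default still covers them.

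The sentence on unknown readings and no evidence of disease might be said to make all missing assessments non-responses. Its bracket points to central-review categories, and a patient who died without a scan has no reading. Taken broadly, it contradicts the multiple-imputation rule that follows it. Either way the text needs reconciling.

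Sensitivity analysis 3 already treats every missing Week 28 assessment as a non-response, and deaths are tabulated separately (SAP 17.2). That limits the harm. But equivalence is declared on the primary analysis, and analysis 3 does not isolate deaths from other missing data.

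Time to event is a different endpoint, so counting all deaths there is not itself a contradiction. It shows only that the plan already treats death as failure elsewhere.

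**Conclusion.** The gap is real but narrow. A death before the Week 28 assessment that is judged unrelated to treatment and not due to progression is unassigned in SAP 16.1.2 and falls to multiple imputation through Protocol 8.8 and the Table 1 footnote. It can then be drawn as a response. Separately, SAP 16.1.1 may let a Week 12 responder who later dies count as a responder with no imputation.

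The likely effect is small: about 0.5 point per imputed death, assuming an imputed probability of 0.77. The 4 v 0 split and the 1% to 3% rates are assumptions. A reader might infer that the rule always favours equivalence. It does so only when the excess deaths fall on the lower-response arm. The population is asymptomatic with ECOG 0 to 1, and the plan allows 4% for drop-out and major deviations together, so many such deaths are not expected.

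This should be fixed before unblinding, because how death enters the primary endpoint ought not to depend on a causality label. It does not undermine the design.

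**What to change.** - Add a stand-alone sentence to SAP 16.1.2 and Protocol 8.8: death from any cause before the Week 28 assessment is a non-response in the primary analysis. Replacing the phrase inside the present SAP bracket would not do, because that sentence applies only after the start of new FL treatment.
- Add the same rule to the footnote of SAP Table 1, which now says nothing about death.
- Limit multiple imputation to patients alive at Week 28 whose missingness is unrelated to treatment.
- Align SAP 16.1.1 with the rule, so that neither evaluation up to death nor the reference to best ORR turns a Week 12 responder who then dies into a Week 28 responder.
- Reconcile the non-responder sentence on unknown readings and no evidence of disease with the multiple-imputation rule.

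The cost is text in two documents. No new data are needed, since deaths are already recorded on their own eCRF page. Observed ORR would be slightly lower in any arm with such deaths. Exact power falls from 84.0% to 82.9%, 81.8% and 80.7% if 1%, 2% and 3% of patients in both arms die this way, about 1 point per 1%. If the deaths fall on one arm only, it is 82.9%, 80.8% and 77.6%. The planned 154 per arm needs no material change unless the deaths are imbalanced.

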### **16.1.3. ANALYSIS OF PRIMARY EFFICACY VARIABLE**

The primary test for statistical equivalence will be performed with respect to SAIT101 versus MabThera® for patients in the FAS. The primary hypothesis is based on the difference in ORR at Week 28 between the two treatments. The equivalence will be declared if the 2-sided 95% CI of the difference in the ORR at Week 28 between treatments (SAIT101 versus MabThera®) is contained within the equivalence margin of [-16.0%, 16.0%] by Cochran-Mantel-Haenszel (CMH) tests. The adjusted proportion difference in ORR and its 95% Newcombe-Wilson CI will be calculated using weighted CMH with stratification factor FLIPI-2 (low, intermediate and high risk).

Descriptive statistics will be presented for the ORR as well as the overall tumor assessment (CR, PR, SD, PD) at planned time points by treatment groups. In addition, a listing of target, non-target and new lesions assessed per IWG criteria 2007 by visit will be also presented.

A bar-chart plot presenting the overall tumor response rate (CR, PR, SD and PD) and the ORR at Week 12 and Week 28, by treatment group, will also be provided.

---

Document:

Author:

Version Number:

Version Date:

Final v1.0

10Sep2019

Template No: CS\_TP\_BS016 Revision 4

Effective Date: 01Apr2016

Reference: CS\_WI\_BS005

**16.1.4. SENSITIVITY ANALYSIS OF PRIMARY EFFICACY VARIABLE**

To assess the robustness of the primary efficacy result, the sensitivity analyses included in Table will be performed.

**Table 1 – Primary analysis and sensitivity analyses for the primary efficacy endpoint**

Analyses for primary endpoint	Analysis Set	Analysis Method	Stratification factors included	Imputation method for missing value at Week 28
Primary analysis	FAS	95% Newcombe-Wilson CI using the CMH weighted method	FLIPI-2 score group	IUDR
Sensitivity analysis 1-1	FAS	Same as primary	Same as primary	No imputation
Sensitivity analysis 1-2	PPS	Same as primary	Same as primary	NA
Sensitivity analysis 2-1	FAS	95% Newcombe-Wilson CI	None	Same as primary
Sensitivity analysis 2-2	PPS	95% Newcombe-Wilson CI	None	NA
Sensitivity analysis 3	FAS	Same as primary	Same as primary	NRI
Sensitivity analysis 4	FAS	Same as primary	Same as primary	MI

Document:  
 Author:

Version Number:  
 Version Date:

Final v1.0  
 10Sep2019

Template No: CS\_TP\_BS016 Revision 4  
 Effective Date: 01Apr2016

Reference: CS\_WI\_BS005

Sensitivity analysis 5-1	FAS	Logistic regression model along with Delta method	Same as primary	Same as primary
Sensitivity analysis 5-2	PPS	Logistic regression model along with Delta method	Same as primary	NA

NRI= Non-responder imputation, MI= multiple imputation; IUDR= imputation using drop-out reason (NRI for missing due to treatment-related reason, MI using logistic regression assuming ignorable missing at random (MAR) for missing due to reasons unrelated to treatment, and no imputation when the reasons are unknown whether they are related to treatment or not).

## 16.2. SECONDARY EFFICACY

### 16.2.1. SECONDARY EFFICACY VARIABLE(S) & DERIVATION(S)

#### ORR at Week 12

The Overall Response Rate (ORR) at Week 12 will be derived as described in section 16.1.1, i.e., similar to the primary endpoint (ORR at Week 28).

#### Time to event (TTE)

The time to event (TTE) is defined as the time from the date of randomization to the date when an event occurs; the following are considered as an event: disease progression evaluated based on tumor assessment done by central imaging review vendor, death due to any cause, or the start of new treatment for FL, whichever comes first.

**Table 2. Outcome and event dates for TTE**

No	Situation	Date of Event or Censoring	Outcome
.			

Document:

Author:

Version Number:

Version Date:

Final v1.0

10Sep2019

Template No: CS\_TP\_BS016 Revision 4

Effective Date: 01Apr2016

Reference: CS\_WI\_BS005

1	No baseline tumor assessment or no post-baseline tumor assessment*	Date of first study drug administration	Censored
2	No progression and no death and no new anticancer treatment	Date of last evaluable tumor assessment (from “Overall Lesion Assessment” CRF page)	Censored
3	Documented progression	Date of first documented progression#	Event
4	Death without progression	Date of death	Event
5	New anticancer treatment started prior to documented disease progression or death on study	Date of first date of new anticancer treatment	Event

\* No baseline tumor assessment means no any target identified and no non-target lesions present at screening captured from “Lesion Assessment with CT Scan” CRF page; no post-baseline means without any assessments by CT scans and evaluated by central review as defined by the IWG Criteria 2007 after study treatment administered.

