2.3.2 Secondary Efficacy Endpoints

Tumor response evaluations as defined by the revised IWG Criteria 2007, for malignant lymphoma (Appendix 4):

- ORR at Week 12
- Complete Response (CR) at Weeks 12 and 28
- Partial Response (PR) at Weeks 12 and 28
- Stable Disease (SD) at Weeks 12 and 28
- Progressive disease (PD) at Weeks 12 and 28
- Time to event (TTE), defined as the time from the date of randomization to the date when an event occurs; an event is disease progression, death due to any cause, or the start of new treatment for FL, whichever comes first

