3.3.1.2 Discontinuation of Study Drug

An individual patient may be discontinued from study drug treatment for the following reasons:

- Prohibited treatment such as any other experimental drug or a concomitant chemotherapy, anticancer hormonal therapy, radiotherapy, or immunotherapy.
- Lack of compliance with protocol (e.g., refusal or inability to adhere to the study schedule or procedures).
- Patients who meet any of the following specific safety discontinuation criteria:
 - Patients who develop severe (common terminology criteria for adverse events [CTCAE] Grade 3 or above) infusion-related reactions, especially severe dyspnea, bronchospasm, or hypoxia, should have the infusion interrupted immediately to receive aggressive symptomatic treatment. In all patients, the infusion should not be restarted on the same day until complete resolution of all symptoms. At this time, the infusion may be initially resumed at the discretion of the Investigator at not more than one-half the previous rate. If the reaction was an anaphylactic reaction, or if the same infusion-related reaction occurs for a second time, the infusion should be permanently discontinued (refer to Section 4.5).
 - Active TB.
 - Invasive fungal infection or opportunistic infection including, but not limited to, listeriosis, legionellosis, or pneumocystis.
 - Hepatitis B virus reactivation or hepatic failure.
 - PML: neurological warning signs include major changes in vision, unusual eye movements, loss of balance or coordination, and disorientation or confusion.
 - Cancer: any new malignant lesion. Patients with basal cell and squamous cell carcinomas of the skin or carcinoma in situ of the cervix uteri that has been excised and cured, may be continued on the study at the discretion of the Investigator. If such carcinomas develop during the study, they may be excised and the patient may continue on the study.
 - Any other AEs which, in the opinion of the Investigator or the Sponsor, could compromise the patient's safety or well-being if they continued to participate in the study.

- Pregnancy in a female participant.

Assessments for patients who discontinue the study drug early

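### SAP Table 2 counts any new anticancer treatment as a TTE event, but the TTE definition it implements counts only new treatment for follicular lymphoma

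*SAP*

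**What the plan says.** Protocol 2.3.2 defines TTE from randomization and states that "an event is disease progression, death due to any cause, or the start of new treatment for FL, whichever comes first". The TTE paragraph in SAP 16.2.1 repeats this, ending "or the start of new treatment for FL, whichever comes first", and adds that progression is judged by central imaging review.

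Table 2, in the same SAP section, sets the dates and outcomes. Two of its rows concern new therapy:

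- Row 5 is an event, dated at the start of therapy: "New anticancer treatment started prior to documented disease progression or death on study".
- Row 2 is censoring at the last evaluable tumor assessment, on the condition "No progression and no death and no new anticancer treatment".

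SAP 2.6 lists the changes from the protocol analysis. They concern the PK and PD analysis sets and one per-protocol exclusion criterion; TTE is not among them. SAP 17.7 lists new anti-lymphoma treatment as a data item. SAP 16.2.3 analyses TTE by Kaplan-Meier curves and a Cox model adjusted for FLIPI-2 group. SAP 16.3 carries the same TTE method over to the exploratory PET-CT analysis.

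**The concern.** The definition and the table give different answers for the same patient. Suppose a patient is in partial response and starts hormonal therapy for another cancer at Week 16. By the definition there is no event, and follow-up continues. By Table 2 the patient fails row 2, meets row 5 and is an event at Week 16. If the same patient later progresses, the definition dates the event at progression and the table dates it earlier.

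A programmer will normally work from the table. TTE would then include events unrelated to lymphoma control, through a widening of the protocol endpoint that nobody has declared.

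**Working it through.** **Wording side by side**

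| Place | Therapy that counts |
|---|---|
| Protocol 2.3.2 | new treatment for FL |
| SAP 16.2.1, TTE definition | new treatment for FL |
| SAP Table 2, row 5 (event) | any new anticancer treatment |
| SAP Table 2, row 2 (censoring) | no new anticancer treatment of any kind |
| SAP 2.6 (changes from protocol) | silent |
| SAP 17.7 (listing) | new anti-lymphoma treatment |

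Rows 2 and 5 use the same wide term, so the table is consistent with itself and inconsistent with the definition.

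**Can the case arise?** Yes. Protocol 3.3.1.2 deals with new malignant lesions and says of certain skin and cervical carcinomas: "If such carcinomas develop during the study, they may be excised and the patient may continue on the study". Protocol 6.5 requires cancers of new histology to be reported as serious adverse events. Whether a simple excision is anticancer treatment is arguable; systemic therapy is the clearer example.

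**The plan's own figures.** There is no event count, hazard ratio, margin or power for TTE to reproduce. The only related figure is the 83% power for overall response rate (ORR) with 154 per arm, 77% in both arms and a margin of 16 points. Exact enumeration with the Newcombe-Wilson interval gives 84.0%, and the Wald approximation gives 83.1%, so the figure reproduces. TTE does not enter it.

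**Number of patients.** The second-cancer treatment rate q by Week 28 is an assumption, 0.5% to 2%.

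- 154 × 0.005 = 0.8 per arm
- 154 × 0.02 = 3.1 per arm

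**Effect on the hazard ratio.** Further assumptions: comparator event risk f by Week 28 of 10% to 30%, true hazard ratio 1.5, and the same q in both arms. With H = −ln(1 − f) and e = −ln(1 − q), the apparent hazard ratio is (1.5H + e)/(H + e). The total number of events is 154 × [(1 − exp(−(H + e))) + (1 − exp(−(1.5H + e)))].

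Example with f = 10% and q = 2%: H = 0.1054 and e = 0.0202, so the ratio is (0.1580 + 0.0202)/(0.1054 + 0.0202) = 0.1782/0.1256 = 1.42.

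| f | Events, FL rule | Events, q = 0.5% | HR | Events, q = 2% | HR |
|---|---|---|---|---|---|
| 10% | 37.9 | 39.3 | 1.48 | 43.3 | 1.42 |
| 20% | 74.6 | 75.8 | 1.49 | 79.3 | 1.46 |
| 30% | 110.0 | 111.0 | 1.49 | 114.0 | 1.47 |

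Across both arms this adds about 1 to 5 events (111.0 − 110.0 = 1.0; 43.3 − 37.9 = 5.4). At q = 3% the lowest apparent ratio is 1.39. If the true ratio is 1, equal extra events leave it at 1.

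**The case against.** The best defence is that the terms are loose synonyms. Table 2 directly follows the definition and exists to implement it. The documents vary their wording for what looks like the same event: Table 1 footnote c of the protocol speaks of anti-lymphoma treatment, and SAP 2.2 of treatment targeting FL. The only new-therapy item listed in SAP 17.7 is lymphoma treatment. Exclusion criteria 3 and 6 and the prohibited treatments in protocol 4.11.2 also keep second-cancer therapy uncommon. This stands as evidence of intent, and it is why the patient *can become* an event rather than certainly does. It does not remove the contradiction, because nothing links Table 2 to the SAP 17.7 item.

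A reader might infer three stronger things that the documents do not support.

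- **That the primary ORR has the same error.** SAP 16.1.1 says "ORR will be evaluated only until the start of subsequent anti-cancer therapy", while the non-responder rule in 16.1.2 begins "Following the start of a new treatment for FL, either due to lack of efficacy or treatment-related toxicity reasons". These rules do different jobs: one limits which assessments count, the other handles missing ones. SAP 16.1.1 also speaks of response up to Week 28 and of best ORR, so an earlier response may be kept. Ending evaluation at systemic therapy for another cancer is a defensible choice of estimand.
- **That no rule in 16.1.2 could apply.** It has a rule for missing responses unrelated to treatment (multiple imputation) and one for missing or non-evaluable assessments (non-responder). Which one applies could be clearer, but the case is not plainly uncovered.
- **That the equivalence test is biased toward success.** TTE has no margin and no equivalence test. For ORR, if 0.5% to 3% of responders in both arms were scored as non-responders, exact power would fall from 84.0% to between 83.4% and 80.7%. Equivalence would become harder to show. That is an upper bound, since 16.1.1 does not itself score them so.

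**Conclusion.** The TTE contradiction is real and the table is wrong as written: rows 2 and 5 use a wider trigger than the protocol and SAP definition, and the change is undeclared. The practical weight is minor. It concerns a secondary endpoint, and the exploratory PET-CT version that borrows its method. The pull toward a hazard ratio of 1 needs a true difference between arms and similar second-cancer rates in both. The patient counts and hazard ratios rest on assumed second-cancer rates, event risks and a true ratio of 1.5, none of which the documents supply. The contradiction in wording depends on none of them. The conclusion does not extend to the primary ORR analysis or its equivalence test.

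**What to change.** In SAP Table 2, rows 2 and 5, replace *new anticancer treatment* with *new treatment for FL*. State that the start date comes from the data behind the SAP 17.7 listing of new anti-lymphoma treatment, and name the eCRF field. The wider Table 2 rule can be kept as an optional sensitivity analysis. If the sponsor does want the wider rule as the main one, SAP 2.6 should declare it as a change from protocol 2.3.2 and the definition in 16.2.1 should be amended to match.

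No change to the ORR rules is needed for this point. The cost is a few words in the SAP and one programming specification. The SAP 17.7 listing indicates that the data are already collected, and the 154 per arm and 83% ORR power are unaffected.
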